#### Sensitivity Analyses

The following sensitivity analyses will be performed to explore the robustness of the primary analysis results and will therefore be performed on both the FAS and PD-L1+ analysis sets. CCI [REDACTED] Unadjusted 95% CI's will be used for all sensitivity analyses of the primary endpoint. The sensitivity analyses will include the following:

- Unstratified analyses will be performed comparing OS between the treatment arms;
  - If the actual number of events is 10% more than the planned number at the primary analysis and the increase is not due to the requirement for at least 18 months of follow-up, i.e. if there are > 392 events in all randomized subjects observed at the prospectively determined cut-off date at the primary analysis, the primary analysis will be repeated, using the first cut-off date at which exactly 356 events in all randomized subjects were observed in the study.
  - The primary analyses will be repeated, censoring those subjects in FAS who received subsequent anti-cancer therapy at the date of the first dose of subsequent anti-cancer therapy minus 1 day.
-

- If the model checks (described later in this section) show large departures from the proportional hazards assumption, the treatment effect on OS outcomes will be additionally explored using restricted mean survival time, discussed in detail in the following subsection.

### **Restricted Mean Survival Time (RMST)**

In the case of large departures from proportional hazards, the primary endpoint of OS will also be analyzed based on restricted mean survival time (RMST) differences (Royston and Parmar 2011 (4)). The RMST methodology is applicable independently of the proportional hazards (PH) assumption and can be used, at a minimum, as a sensitivity analysis to explore the robustness of the primary analysis results.

The RMST to cut-off time  $\tau$  can be interpreted as the expected survival time among all patients followed to, at most, time  $\tau$ . The RMST analysis hinges on the selection of the cut-off point ( $\tau$ ). It is noted that the cut-off point should not exceed the minimum of the largest observed time (event or censoring) for both treatment arms, in order for the RMST to be adequately estimated for both and comparison between them to be appropriate.  $\tau$  should be clinically meaningful and closer to the end of the study follow-up, so that the majority of survival outcomes will be observed within the time interval. Thus, the selection of  $\tau$  should ensure that the RMST evaluation does not exceed the maximum evaluable time point, but should also seek to maximize  $\tau$ , in order to provide a meaningful assessment of treatment effect. To avoid arbitrary selection of the common cut-off  $\tau$  (used for both treatment arms), the following analyses will be performed:

- $\tau_1$  = minimum of (largest observed survival time for avelumab + BSC arm, largest observed survival time for chemotherapy/BSC-only arm).
- $\tau_2$  = minimum of (largest survival event time for avelumab + BSC arm, largest survival event time for chemotherapy/BSC-only arm).

The treatment effect between the two treatment arms will be assessed based on the difference in RMST. The associated 95% CI for the difference in means and a 2-sided p-value will be generated.

### **Methods for Evaluating the Validity of Model Assumptions**

Proportional Hazards Assumption:

- The proportional hazards assumption will be checked visually for the primary analysis by plotting  $\log(-\log(OS))$  versus  $\log(\text{time})$ , within each randomization stratum by treatment group.
- Schoenfeld residuals including a LOESS curve will be plotted to graphically investigate any violations of the proportional hazards assumption. Schoenfeld residuals will be computed in SAS using the PHREG procedure via the OUTPUT statement (keyword=RESSCH). With proportional hazards, the LOESS curve should be approximately parallel to the x-axis.

#### 15.1.4 Subgroup Analysis of Primary Endpoint

*Analysis sets: FAS, PD-L1+*

Subgroup analyses will be performed on the primary endpoint for all subgroup levels defined in Section 9 “Subgroup Analysis Sets”. CCI

No adjustment for multiplicity will be performed. The two treatment arms will be compared using a two-sided unstratified log rank test for each subgroup level. The unstratified HR of avelumab over chemotherapy/BSC-only and its corresponding 95% CI will be computed at each

---

subgroup level. In the case of a low number of subjects within a category (<5% of the randomized population), the categories may be pooled.

The HR and its corresponding 95% CI, overall and for each subgroup level will be presented in a forest plot.

To assess the heterogeneity of treatment effect on OS across the subgroup levels, two Cox regression models will be fitted for each combination of subgroup/primary endpoint. Both models will use subgroup and treatment arm as explanatory variables; the treatment-by-subgroup interaction will be included in the second.

- Model 1: treatment + subgroup
- Model 2: treatment + subgroup + treatment \* subgroup-variable

A p-value for the interaction test (Likelihood Ratio test) will be provided together with the subgroup HR (analysis subgroup level over reference category), point estimate of the regression parameter, and corresponding 95% CI of the interaction model parameter.

### **15.1.5 Time of Follow-up for Primary Endpoint**

*Analysis sets: FAS, PD-L1+*

In order to compare median time of follow-up for overall survival, Kaplan Meier estimates will be calculated for both treatment groups using the following censoring rules (reverse censoring indicator):

Subjects alive or lost to follow-up	Time from randomization to last date known to be alive	No censoring
Subjects who died	Time from randomization to date of death	Censored

Kaplan-Meier estimates (product-limit estimates) will be presented by treatment group together with the median time of FU.

### **15.2 Secondary Endpoint Analyses**

Based on the hierarchical testing strategy described in Section 15, at the primary analysis, PFS and BOR will be tested in primary analysis if, and only if, of hypothesis testing for OS in both all randomized subjects and PD-L1+ subjects reaches statistical significance.

### 15.2.1 Progression-Free Survival

*Analysis sets: FAS, PP Analysis Set*

PFS is defined as the time from the date of randomization to the date of the first documentation of objective progression of disease (PD) or death due to any cause, whichever occurs first. The tumor response will be determined according to RECIST 1.1 per investigator assessment and is measured relative to the Re-Baseline scan.

$$\text{PFS time (in months)} = (\text{Date of PD or death or censoring} - \text{date of randomization} + 1) / 30.4375$$

PFS data will be censored on the date of the last adequate tumor assessment for subjects who do not have an event (PD or death), for subjects who start a new anti-cancer therapy (of any kind) prior to an event, or for subjects with an event after two or more missing tumor assessments. Subjects who do not have a Maintenance Phase baseline tumor assessment (as defined in Section 10) or who do not have any post-baseline tumor assessments will be censored on the date of randomization unless death occurred on or before the time of the second planned tumor assessment, in which case the death will be considered an event.

If a tumor assessment was performed on the same day as start of new anti-cancer therapy, it will be assumed that the tumor assessment was performed prior to the start of the new anti-cancer therapy, therefore the tumor assessment will be included in the derivation of the PFS time.

Last adequate tumor assessment is defined as the last tumor assessment result that is not “NE” or “NA”.

The censoring and event date options to be considered for the PFS and DR analysis are presented in Table 4.

**Table 4 Outcome and Event Dates for PFS Analyses**

Scenario	Date of event/censoring	Outcome
No Maintenance Phase baseline assessment a	Date of randomization	Censored b
PD or death $\leq$ 12 weeks after Maintenance Phase randomization or $\leq$ 2*(scheduled time between tumor assessments) d	Date of progression or death	Event
PD or death $>$ 2*(scheduled time between tumor assessments) d	Date of last adequate tumor assessment	Censored
PD or death after 2 or more missing or inadequate post-baseline tumor assessments	Date of last adequate tumor assessment c	Censored
No PD and no death	Date of last adequate tumor assessment c	Censored

Treatment discontinuation due to 'Disease progression' without documented progression	Not applicable	Information collected on treatment discontinuation page is ignored since outcome should be derived based on documented progression only. General censoring rule is applied.
New anti-cancer therapy given	Date of last adequate tumor assessment before anti-cancer therapy is given	Censored

a Subjects whose baseline scan is outside of the RECIST defined window (28 days prior to randomization) will be treated as if they had no baseline and will be censored on the day of randomization

b However, if the subject dies  $\leq 12$  weeks after randomization the death is an event with date on death date

c If there are no adequate post-baseline assessments prior to PD, death, or subsequent anti-cancer therapy, then the observation will be censored on the date of randomization.

d Per protocol, subjects are to receive tumor scans once every six weeks during the first 12 months of the Maintenance Phase and every 12 weeks thereafter.

The analysis of PFS will be analogous to that for OS time as described in Section 15.1.1. There is no interim analysis planned for PFS.

The treatment effect on PFS time will be estimated using the same approach as OS analysis. The hazard ratio of avelumab versus chemotherapy/BSC (with chemotherapy/BSC as reference) together with the corresponding Wald two-sided 95% CIs will be presented.

Kaplan-Meier estimates (product-limit estimates) will be presented by treatment group together with a summary of associated statistics including the median survival time with two-sided 95% CIs. In particular, the progression-free survival rate at 3, 6, 9, 12, 15, 18, 21, and 24 months will be estimated with corresponding two-sided 95% CIs. The CIs for the median will be calculated using the same approach as OS analysis.

Frequency (number and percentage) of subjects with each event type (PD or death) and censoring reasons will be presented by treatment arm. Censoring reasons are as follows:

- Administrative Censoring: Ongoing in the study without an event
- Non-Administrative Censoring:
  - No baseline assessment
  - No post-baseline assessment
  - Start of new anti-cancer therapy
  - Event after 2 or more missing assessments
  - Withdrawal of consent
  - Lost to follow-up

Lost to follow-up will include the following subjects:

- Lost to follow-up status is collected on the eCRF page prior to the analysis cut-off;
- Two or more missed or inadequate post-baseline tumor assessments immediately preceding analysis cut-off date.

The PFS time or censoring time and the reasons for censoring will also be presented in a subject listing.

The primary analyses will be repeated on the PP analysis set if the PP analysis set includes less than 90% of subjects in the FAS.

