8.3.2.1 Progression-Free Survival

Progression-Free Survival, defined as the time (in months) from randomization to the date of the first documentation of objective PD or death due to any cause (whichever occurs first), is the first key secondary endpoint of the study. The date of the first documented objective PD will be determined according to RECIST v1.1 based on Investigator response assessment.

The PFS data will be censored on the date of the last adequate tumor assessment for subjects who do not have an event (PD or death), for subjects who start new anticancer treatment prior to an event, or for subjects with an event after 2 or more missing tumor assessments. Subjects who do not have a baseline tumor assessment or who do not have any post-baseline tumor assessments will be censored on the date of randomization unless death occurred on or before the time of the second planned tumor assessment, in which case the death will be considered an event.

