6-weekly tumor evaluation/staging imaging scan (CT/MRI) not performed at all	PROCED13	
6 weekly Tumor Evaluation/Staging imaging scan (CT/MRI) performed >10 days outside window	PROCED14	
Paper QoL used and the data were moved from the paper QoL to the tablet by the site staff	PROCED16	
Subject randomized despite having disease progression assessed by the independent radiologist	PROCED20	Yes
Laboratory		
Subject enrolled or randomized without all safety lab results available (including pregnancy test for females)	LABPRCO01	
Subject dosed without all safety lab results available (including pregnancy test for females) or not reviewed by the Investigator prior to dosing	LABPRCO02	
Randomization		
Randomization interrupted in IWRS resulting in erroneous application of the randomization code	RANDOM01	Yes
Patient randomized more than once	RANDOM02	
Other		
Any other protocol deviation which is deemed to be significant for a specific subject or for the trial but has not been pre-specified in this table	OTHPRC01/ OTHPRC02	

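### SAP Table 4 censors PFS events on elapsed time alone, which conflicts with the rule of two or more missing assessments when exactly one scan is missed

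*SAP*

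**What the plan says.** Two kinds of rule deal with PFS events that follow missed scans.

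**Count of missed scans**
- Protocol 8.3.2.1 censors at the last adequate assessment "or for subjects with an event after 2 or more missing tumor assessments".
- The SAP 15.2.1 text says the same: "or for subjects with an event after two or more missing tumor assessments".
- One row of SAP Table 4 censors "PD or death after 2 or more missing or inadequate post-baseline tumor assessments".
- The censoring reasons listed after Table 4 include "Event after 2 or more missing assessments".

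**Elapsed time**
- A separate row of Table 4 censors "PD or death $>$ 2*(scheduled time between tumor assessments" (closing bracket omitted) at the last adequate assessment. It contains no count of missed scans.
- The matching event row covers PD or death within 12 weeks of randomization or within twice the scheduled interval.

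Footnote d gives the scan schedule: "once every six weeks during the first 12 months of the Maintenance Phase and every 12 weeks thereafter". SAP Section 8 states that the methods follow protocol version 7.0 with one exception, which concerns the treatment start date of BSC-only subjects. The elapsed-time row is not mentioned there.

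**The concern.** If one scan is missed and the scans on either side fall on different days of their windows, the interval between them can exceed twice the scheduled interval although only one assessment is missing. The same subject is then an event at the PD date under the text, or is censored about 12 weeks earlier under the table, depending on which line is programmed. A subject censored only by the time row has no accurate label in the list of censoring reasons, because the reason for missed scans there requires two or more. PFS is the first key secondary endpoint in the testing hierarchy, so its event rule should have one reading before the database is locked.

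**Working it through.** **Inputs**
- Interval: 42 days in the first 12 months, then 84 days (Table 4, footnote d).
- On-treatment scan window: 5 days early to 0 days late (Protocol 7.1.4).
- Follow-up scan window: 7 days either side (Protocol 7.1.7).
- Targets are taken as fixed, because Protocol 7.1.4 returns subjects to the target date after an off-schedule visit.
- Time is counted from the last adequate assessment, the date that the row uses for censoring.

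**The plan's own figure.** 2 × 6 weeks = 12 weeks = 84 days, which reproduces the 12 weeks in the event row. For 12-weekly scans, 2 × 84 = 168 days.

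**Gap from last adequate scan to PD scan.** Gap = interval × (missed + 1) + d2 − d1, where d1 and d2 are the deviations from target at the last adequate scan and at the PD scan.

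| 6-weekly schedule, limit 84 days | On treatment | Follow-up | Count rule |
|---|---|---|---|
| None missed | 37–47 | 28–56 | event |
| One missed | 79–89 | 70–98 | event |
| Two missed | 121–131 | 112–140 | censored |

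For PD found at a scheduled scan within one schedule, the two rules disagree only in the middle line. Example: adequate scan on day 37 (5 days early), week 12 missed, PD on day 126. The gap is 126 − 37 = 89 days. Under the text this is an event at day 126. Under the time row it is censored at day 37. On the 12-weekly schedule the corresponding one-missed gaps are 163–173 and 154–182 days against 168.

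**On-target scans.** By simple subtraction, one missed scan gives 126 − 42 = 84 days, and the rules agree. Under the default duration convention in SAP Section 10 (difference plus 1), the same case is 85 days and would be censored. The same paragraph counts time since an event without the plus 1, and Table 4 does not say which applies.

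**Share of one-missed PDs with a gap above 84 days.** By symmetry this is P(d2 > d1) = (1 − Σp²)/2, where p is the probability of each scan day. The spread of scan days is an assumption.
- All on target: 0.
- 90% on target, the rest spread evenly: 0.094 on treatment, 0.095 in follow-up.
- 80% on target: 0.176 and 0.179.
- Uniform in the window: 15/36 = 0.417 and 105/225 = 0.467.

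**Subjects affected.** With miss rate m per scan, the share of PDs at week 18 or later is m(1 − m) × P. The documents give no miss rate or PD count, so take m from 2% to 10% and 400 such PDs.
- m = 0.02, P = 0.094: 0.0196 × 0.094 = 0.18%, under 1 subject.
- m = 0.10, P = 0.417: 0.09 × 0.417 = 3.75%, or 15 subjects.
- If only 200 PDs are that late, the second figure halves to 7.5.

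**Two further ambiguities**
- The row does not say which interval applies across the change at month 12. If scans fall at weeks 42, 48 and 60 (an assumption) and week 48 is missed, the gap is 18 × 7 = 126 days on target: over 84, under 168.
- The count row and the lost-to-follow-up definition ("Two or more missed or inadequate post-baseline tumor assessments immediately preceding analysis cut-off date") include inadequate scans. The protocol and the SAP text say only missing. With the last adequate scan on day 42, NE scans on days 84 and 121, and death on day 125, the gap is 83 days, which fits the event row, while two inadequate scans fit the censoring row.

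**The case against.** The time row is most plausibly a programmable version of the two-missed rule. It matches that rule when scans fall on target. The reasons for a non-evaluable best response in SAP 15.2.2 use similar 12-week logic. If scan dates were re-anchored to the previous actual scan, one missed scan on treatment could not exceed 84 days, although follow-up could still reach 91. Protocol 8.5.1 lets the SAP modify planned analyses. The PFS test is also remote: it needs both OS hypotheses rejected, and the protocol's amendment rationale reports PD-L1 positivity below 15% with substantially reduced power. PFS sensitivity analysis 2 counts every PD and death regardless of missing assessments.

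The points on consequence stand. Intent does not remove the conflict: Protocol 7.1.4 points to fixed targets, and the text and the table then classify the same compliant subject differently.

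Four stronger readings are tempting and are not supported:
- *The row censors every event after 12 weeks from randomization.* Its date column names the last adequate assessment, which implies the origin.
- *The two censoring rows need a precedence rule.* Both give the same outcome on the same date, so their order does not matter.
- *The plan lacks scan weeks around month 12.* The response-assessment parts of the protocol's schedule tables are redacted, so they may be stated there. Only the row's silence on the interval can be criticized.
- *Nearly half of PDs are misclassified, or one arm is favored.* The 42% and 47% apply only to PDs found after exactly one missed scan, with scan days assumed uniform. Nothing shows that the arms differ.

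**Conclusion.** The elapsed-time row departs from the protocol's censoring rule and from the SAP's own text, and the departure is undeclared. For PD at a scheduled scan within one schedule, the conflict is confined to exactly one missed scan with a gap above twice the interval. That can happen with every performed scan inside its window. The size runs from nil (all scans on target, simple subtraction) to about 15 of an assumed 400 PDs at week 18 or later (10% miss rate, uniform on-treatment windows). Miss rate, scan-day spread and PD count are all assumptions. The primary OS analyses are untouched and no direction of bias is shown. The change is cheap and should be made before lock, but it does not threaten the trial's main conclusions.

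A separate, minor point: the visible list of PFS sensitivity analyses in SAP 15.2.1 omits the analysis in Protocol 8.5.3.1 that counts clinical progression as an event, and Section 8 does not declare its removal.

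**What to change.** In SAP Table 4 and the related text:

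1. Delete the elapsed-time censoring row.
2. Make the event row read: *PD or death ≤ 12 weeks after randomization, or after at most one missing assessment*. Leave the existing rule for subjects with no post-baseline scan in place and apply it first.
3. Use one definition of a missing scan for PD and death. A scheduled scan is missing if no scan was done within its window plus a 10-day tolerance, and that period had ended before the PD or death date. The tolerance is the one already used in Appendix I ("6 weekly Tumor Evaluation/Staging imaging scan (CT/MRI) performed >10 days outside window"). That entry names 6-weekly scans, so say explicitly that it also covers 12-weekly ones.
4. State once whether NE scans count as missing, with the same wording in the text, Table 4 and the censoring reasons. If they count, declare it in Section 8.
5. Reinstate the clinical-progression sensitivity analysis, or declare its removal in Section 8.

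Check of item 3 on treatment: the week-12 period is days 69–94 and the week-18 period is days 111–136. In the day 37 to day 126 example, one scan is missing, so PD is an event. With an adequate scan on day 42, none at weeks 12 or 18, and an unscheduled PD scan on day 146 (allowed by Protocol 7.3), two are missing and PD is censored. With the same history, PD or death on day 127 counts one missing, and both are events.

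Do not assign scans to the nearest due date instead. The day-146 scan is 20 days from day 126 and 22 from day 168, so it would count as the week-18 scan and PD would be an event. A death on day 127 with the same history would be censored if week 18 counts as missed once its window closes on day 126.

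The cost is SAP wording and a small programming change, with no new data. SAP 7.3 bars database lock until the SAP is approved, so the change can precede lock.

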### **Sensitivity Analysis**

The following sensitivity analyses will be performed to explore the robustness of the primary analysis results. CCI [REDACTED] Unadjusted 95% CI's will be used for all sensitivity analyses. The sensitivity analyses will include the following:

1. Unstratified analyses will be performed, comparing PFS time between the treatment arms;
2. Counting all PD and deaths as events regardless of missing assessments or timing of the event;
3. PFS based on investigator assessment wherein initiation of subsequent anticancer therapies is not used as a censoring reason for PFS;
4. In the case of large deviations from proportional hazards, treatment effect on PFS outcomes will be additionally explored using restricted mean survival time, discussed in detail in Section 15.1.2.

